4.2 Endpoints

4.2.1 Descriptive Endpoints – During Study Period

- The mean change in HbA1c will be presented from baseline to end of study
- Change of Total Daily Dose (TDD) of insulin from baseline to end of study
- Change of weight from baseline to end of study
- Time spent in Auto Mode versus time spent in Manual Mode
- Time in different range (% of SG): SG < 50, 54, 60, 70 mg/dL, SG > 140, 180, 250 mg/dL, 350 mg/dL
- Number of Events, Area Under Curve (AUC) and Time in the hyperglycemic range: sensor glucose (SG) > 140, 180, 250, 350 mg/dL
- Number of Events, AUC and Time in the hypoglycemic range: SG < 50, 54, 60, and 70 mg/dL
- Change in BG values during meal challenge (BG prior and BG 2 hours after meal)
- Change in % of time in euglycemia (70-180 mg/dL) during meal challenge, prior and 2 hours after meal
- Difference in AUC during meal challenge prior and 2 hours after meal
- Subgroup analysis will be performed for:
 - Age
 - 7-13
 - 14-75
 - Setpoint
 - 100 mg/dL
 - 120 mg/dL

- Temp Target usage
 - Yes
 - No

4.2.2 Descriptive Endpoints – During Continued Access Period

Descriptive Endpoints for Continued Access

- Time in Target Range (TIR, 70 – 180 mg/dL)
- Time Below Range (TBR, SG < 70 mg/dL)
- Time Above Range (TAR, SG > 180 mg/dL)
- Time in different range (% of SG): SG < 54, 60 mg/dL, SG > 140, 250 mg/dL, 350 mg/dL
- Number of Events, Area Under Curve (AUC) and Time in the hyperglycemic range: sensor glucose (SG) > 140, 180, 250, 350 mg/dL
- Number of Events, AUC and Time in the hypoglycemic range: SG < 54, 60, and 70 mg/dL
- Time spent in Auto Mode versus time spent in Manual Mode
- The mean change in HbA1c, if applicable
- Change of Total Daily Dose (TDD) of insulin

4.2.3 Safety Endpoint – During Study Period and Continued Access

- Serious Adverse Events (SAE)
- Serious Adverse Device Effects (SADE)
- Unanticipated Adverse Device Effects (UADE)
- Incidence of Severe Hypoglycemia
- Incidence of DKA

4.2.4 Device Deficiencies – During Study Period and Continued Access

Descriptive summary will be used to characterize device deficiencies:

- All reports of device issues.

4.2.5 Subject Feedback

Descriptive summary will be used to characterize study questionnaire results. Refer to CIP321 AHCL Questionnaire Guide for administration details.

5. Investigation Plan

[figure not shown]
This study is a multi-center, single arm study in insulin-requiring adult and pediatric subjects with type 1 diabetes. The study period will be approximately 90 days long. It will be followed by a continued access period, during which subjects who have completed the entire study period will be given the opportunity to continue using investigational study devices until those devices are approved by the FDA for commercial use and are commercially available. They will be provided with a revised consent form and will sign it prior to continuing. Subjects who have already completed the study period will be given the opportunity to re-enter the study, if they elect to continue using the system. They will also sign the revised consent form.

A total of up to 350 subjects (aged 7-75) will be enrolled at up to 30 investigational centers in the US in order to achieve the following:

- N=125 subjects 14-75 years of age with type 1 diabetes who will complete the study
- N=125 subjects 7-13 years of age with type 1 diabetes who will complete the study

Staged enrollment:

- Subjects 7-13 years of age may be enrolled after N=15 subjects 14-75 years with type 1 diabetes have finished 30 days of the study period. The Data Monitoring Committee (DMC) will review the subjects' data. Enrollment of subjects 7-13 years of age may begin after DMC approval.

Overview of the Run-in and Study Periods:

Run-in Period:

The run-in period will be used to allow subjects to become familiar with new study devices. During the run-in period study subjects will be using the Study Pump (MiniMed™ 670G, version 4.0 AHCL) with only the Sensor Augmented Pump function activated (i.e. SmartGuard™ Auto Mode is turned OFF). All subjects and their caregivers will be trained on diabetes management principles, such as the treatment of hyperglycemia and hypoglycemia. In addition, there will be training regarding the need to have access to oral glucose and glucagon in case of hypoglycemia.

For study purposes, subjects will be instructed to perform SMBG if they are experiencing a severe hypoglycemic event, severe hyperglycemic event or Diabetic Ketoacidosis (DKA). As a precaution, subjects will be told that they should keep their own insulin pump supplies in a safe place and to have back up supplies on hand (such as insulin and syringe) in the event they are asked to revert back to their own therapy during the study or experience study pump issues (i.e. infusion set occlusion with high glucose).

Subjects will be instructed to insert glucose sensors only in the locations that are specified in the User Guide materials. Reminders will be given to subjects at each office visit. Information about sensor insertions will be collected on an electronic case report form (eCRF) in the study database, i.e. insertion location.

Regular Sized Dinner Challenge with Missed Meal Bolus:

On the day prior to attending Visit 5, while subjects are in manual mode with CGM, they will be asked to consume dinner without administration of a Meal Bolus. The size of the meal should be their standard amount. Subjects will be asked to check BG at the start of the meal, as well as 2 hours and 4 hours after the meal and provide correction as necessary. Content and timing of the meal, along with BG values, will be recorded on the Meal Challenge log. This missed dinner bolus challenge should only start if the following conditions are met:

- SMBG at start of meal is ≤ 200 mg/dL
- Sensor glucose is available.

Study Period:

Having met all criteria, subjects will proceed to the study period, which begins at Visit 5. All subjects will continue using the study pump and will use Auto Mode for 90 days during the study period.

Subjects should use the system in Auto Mode at all times. If subjects are exited from Auto Mode, they should try to mitigate and return to Auto Mode as soon as possible. During times when subjects are not able to use Auto Mode, they should use the remaining SmartGuard™ features (i.e. Suspend before Low).

Setpoint in the study pump:

The sponsor will provide guidance on the starting setpoint for subjects based on cohorts listed below:

- A minimum of 50 subjects 14 years of age and older will start the study with an Auto Basal setpoint of 100 mg/dL. They will switch to the 120 mg/dL setpoint after 45 days (± 5 days) of the study period.

- A minimum of 50 subjects 14 years of age and older will start the study with an Auto Basal setpoint of 120 mg/dL. They will switch to the 100 mg/dL setpoint after 45 days (\pm 5 days) of the study period.
- A minimum of 50 subjects 7-13 years of age will start the study with an Auto Basal setpoint of 100 mg/dL. They will switch to the 120 mg/dL setpoint after 45 days (\pm 5 days) of the study period.
- A minimum of 50 subjects 7-13 years of age will start the study with an Auto Basal setpoint of 120 mg/dL. They will switch to the 100 mg/dL setpoint after 45 days (\pm 5 days) of the study period.

The investigator has the discretion to start subjects at either the 100 mg/dL or 120 mg/dL setpoints, while the Sponsor will ensure that the required minima for each setpoint are being met. Regardless of which setpoint is being set at the beginning of the study period, subjects should attempt to change the setpoint after 45 days (\pm 5 days) of the study period. For example: A subject who starts at the 100 mg/dL setpoint, should attempt to change the setpoint to 120 mg/dL after 45 days.

Meal challenges (Run-in and Study period):

The table below summarizes all meal challenges in the study.

- All meal challenges should only start if the following conditions are met:
 - SMBG at start of meal is \leq 200 mg/dL
 - Sensor glucose is available.

Run-in period; Regular sized meal with missed Meal Bolus challenge				
Timing	Type of challenge	Day	Meal(s)	Notes
Run-in	Missed Meal Bolus (regular sized meal)	Day prior to V5	Regular sized Dinner	If the subject qualified to stay in Auto Mode during the Run-In Period, they must turn off Auto Mode for at least 6 hours prior to the start of the Missed Meal Bolus Challenge.
Study period; Meal challenges				
Setpoint	Type of challenge		Meal(s)	Notes

Study Period (100 mg/dL setpoint)	Large sized meals	Day 1	Large sized Breakfast and Large sized Dinner	Meal composition, meal size and time of meal consumption should match meals at Setpoint of 120 mg/dL.
Study Period (100 mg/dL setpoint)	Large sized meals	Day 2	Large sized Breakfast and Large sized Dinner	Meal composition, meal size and time of meal consumption should match meals at Setpoint of 120 mg/dL.
Study Period (100 mg/dL setpoint)	Large sized meal	Day 3	Large sized Breakfast	Meal composition, meal size and time of meal consumption should match meal at Setpoint of 120 mg/dL.
	Missed Meal Bolus		Regular sized dinner meal	Meal composition, meal size and time of meal consumption should match Run-in period meal
Study Period (100 mg/dL setpoint)	Missed Meal Bolus with Large sized meal	Day 4	Large sized Dinner	Meal composition, meal size and time of meal consumption should match meal at Setpoint of 120 mg/dL.
Study Period (120 mg/dL setpoint)	Large sized meals	Day 1	Large sized Breakfast and Large sized Dinner	Meal composition, meal size and time of meal consumption should match meals at Setpoint of 100 mg/dL.
Study Period (120 mg/dL setpoint)	Large sized meals	Day 2	Large sized Breakfast and Large sized Dinner	Meal composition, meal size and time of meal consumption should match meals at Setpoint of 100 mg/dL.
Study Period (120 mg/dL setpoint)	Large sized meal	Day 3	Large sized Breakfast	Meal composition, meal size and time of meal consumption should match meal at Setpoint of 100 mg/dL.
	Missed Meal Bolus		Regular sized dinner meal	Meal composition, meal size and time of meal consumption should match Run-in period meal
Study Period (120 mg/dL setpoint)	Missed Meal Bolus with Large sized meal	Day 4	Large sized Dinner	Meal composition, meal size and time of meal consumption should match meal at Setpoint of 100 mg/dL.

- **Regular Sized Dinner Challenge with Missed Meal Bolus**

During the study period, once at each Auto Basal setpoint (i.e. 120 mg/dL and 100 md/dL) on Day 3 of the multi-day meal challenge, subjects will be asked to consume the **same regular sized dinner that they had during the run-in period**. For example, if the dinner meal was consumed without an insulin bolus for the meal at 5 pm during the run-in period, that same dinner meal should be consumed at approximately the same time on Day 3 at each setpoint during the study period. Subjects will be asked to check BG at the start of the meal, as well as 2 hours and 4 hours after the start of the meal and provide correction as necessary. Details should be recorded, along with BG values, on the Meal Challenge log.

- **Large sized Meal Challenges:**

On large sized meal challenge days, all subjects will be instructed to eat at least 1 meal with at least 50% higher caloric intake including 50% more carbohydrates and 50% higher in fat than what the subject reports that he/she usually eats. It is recommended that subjects eat food at restaurants or consume prepared meals (e.g. things like turkey and stuffing), which have not been eaten during the last month. A log will be used to collect information about type of food, name of restaurant (if applicable), confirmation that the meal eaten was different from any meal eaten within the last month and confirmation that meal size was at least 50% more than when subjects usually consume in terms of calories, carbohydrates and fat. The log should also contain the time and date of the meal, as well as confirmation that a BG was taken at the start of the meal, 2 hours after the start of the meal and 4 hours after the start of the meal. The timing of the meal challenges will be at the investigator's discretion. The subject's companion must be physically present in the same building, home or location (if not at home) during the meal challenge (and for 4 hours following the start of the meal), must be able to check SMBG (in case it is needed) and give glucose/administer glucagon as needed. This challenge will include a missed Meal Bolus on Day 4. See Table above.

Exercise Challenges (Study Period):

The following exercise challenges should occur during the study period:

- 3 consecutive days of exercise challenge at setpoint of 100 mg/dL
- 3 consecutive days of exercise challenge at setpoint of 120 mg/dL

- **Exercise Challenges Details**

On exercise challenge days, all subjects will be required to engage in 1-2 hours of physical exercise each day. During this time, subjects should use the Auto Basal setpoint target of

100 mg/dL or 120 mg/dL (depending on what is required at that time of the study period), unless a subject prefers to use the 150 mg/dL target before, during and immediately after the exercise challenges. For the remainder of days, the temporary target will be set at the Investigator's discretion. A log will be used to collect information about exercise type, date, time (start and finish of exercise), duration and name of the companion. The log should also contain confirmation that SMBG was done at the beginning of exercise, as well as 2 and 4 hours after the start of the exercise. The timing of the exercise challenge will be at the investigator's discretion. A photograph should be taken on each day of the exercise to indicate that exercise took place. Subjects may also use a Smart Phone application to document their exercise. The subject's companion must be physically present in the same building, home or location (if not at home) during the exercise challenge, must be able to check SMBG (in case it is needed) and give glucose/administer glucagon as needed. Examples of types of exercise include but are not limited to:

- Running
- Cycling
- Swimming
- Hiking
- Walking
- Games (e.g. Wii interactive video games)
- Indoor/outdoor playground (Pediatric subjects)
- Yoga/stretching
- Any sport activity which involves ongoing physical movement (i.e., tennis, golf, basketball, tee ball or volleyball)
- Dancing
- Zumba
- Aerobics
- Spinning

Continued Access period:

At the end of the study period, subjects will have the opportunity to continue using the AHCL system at home until the Sponsor receives FDA approval to commercialize the products and system is commercially available. During the continued access period, subjects will be asked to use the system as intended and to upload device data on a weekly basis. See Visit Schedule tables for frequency of device uploading. Office visits will be required at 3 month intervals.

Continued Access Period expansion:

During the continued access period, all participating subjects will transition from the 670G system, version 4.0 AHCL, to the 780G system which features Bluetooth® connectivity. The CGM used with 780G will be Guardian™ 4 Transmitter with the Guardian™ Sensor (4). Subjects will continue to use the 780G system at home until the sponsor notifies sites to end subjects' study participation. The MiniMed™ Clinical App and the Medtronic CareLink™ Clinical App will be used by subjects when they are available.

SMBG recommendations:

Typically, one SMBG is required every 12 hours for calibration. Routine SMBG is not required. Occasionally, subjects may receive a notification if the pump needs a BG to enter or stay in Auto Mode. For study purposes, subjects will be instructed to perform SMBG if they are feeling low (but sensor glucose is not low) and if they are experiencing a severe hypoglycemic event, a severe hyperglycemic event or DKA.

Companions:

Subjects will be required to have a companion who resides (or will live) in the same building (or home) during the proposed study at night, and also to be physically present in the same building, home or location (if not at home) during the exercise and meal challenges. A companion should be present during meal challenges and for 4 hours following the start of the meal. Companions should be able to check SMBG (in case it is needed), give glucose or administer glucagon.

5.1 Duration

The study is anticipated to last no longer than 18 months from investigational center initiation to completion of all data entry and monitoring procedures. The study will target 6 months to complete subject enrollment. Subjects can expect to participate for approximately 4-5 months between the run-in period and study period. The continued access period may lengthen the overall duration of the study considerably.

5.2 Rationale

The design of this study as a single arm trial with safety and effectiveness endpoints represents the next step in the development of a closed loop insulin delivery system. Iterative changes in the control algorithm, which include additional levels of automation, require a study design equivalent to the design that was approved in the study of the predecessor MiniMed™ 670G system.

6. Determination of Sample Size

A total of up to 350 subjects (aged 7-75) will be enrolled at up to 30 investigational centers in the US in order to reach 250 subjects who will complete the study (125 for 14-75 years old and 125 for 7-13 years old).

7. Statistical Methods

7.1 Study Subjects

7.1.1 Disposition of Subjects

The number of subjects enrolled in the study will be presented. The reasons for discontinuing prior to study completion will be summarized.

7.1.2 Clinical Investigation Plan (CIP) Deviations

All protocol deviations will be presented in the listings.

7.1.3 Analysis Sets

- Intention to Treat (ITT) Population

The Intention to Treat (ITT) population will include all subjects who start the study period (which means subjects must enter auto mode).

- Per Protocol (PP) Population

The Per Protocol (PP) population will include all subjects who complete the study period, are in Auto Mode \geq 80% of the time and without major deviations.

- Efficacy Population

The primary analysis will be performed on the ITT population. Sensitivity analysis will be performed on PP population.

- Safety Population

The Safety Population will include all enrolled subjects (subjects who signed inform consent form).

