# 7.2. Subject Enrollment

Subjects will be considered enrolled in the study upon signing the Informed Consent Form (ICF)/ Assent Form.

A subject will be assigned a unique study subject ID (SID) via the eCRF, which is a 9-digit code (321XXXXX). The first three numbers refer to the CIP number (321), the next three numbers refer to the investigational center number, and the last 3 numbers refer to the subject number assigned during Visit 1 (e.g., 321002001 is subject 001 from site 002).

The investigator will maintain a log of all subjects enrolled in the clinical study, assigning a SID linked to their names, alternative SID, and contact information.

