# 9.3. Study Visit Schedule & Scheduled Follow-Up Visit Windows

### Run-in Period Visits: To be completed in 45 days

- Screening Visit 1 (Office): Consent and Screening
- Run-in Visit 2 (Office): Day 7 after Visit 1 (+3 days)
  - Eligibility has been confirmed
  - Start Study Pump
    - Pump Training
  - Start CGM (if using SAP prior to Screening)
    - If SAP using Suspend on Low/Predictive Suspend before Low prior to Screening, those features may be used from Visit 2
    - CGM Training, if applicable
- Run-in Visit 3 (Office): Day 0 after Visit 2 (+7 days)
  - Start CGM (if not already started at Visit 2)
  - Start 2 weeks of measured sensor wear period
    - System is used in manual Mode by subjects who are not using Auto Mode with 670G at Screening
      - SmartGuard™ features (Suspend on Low, Predictive Suspend before Low) may be activated
    - SAP subjects using Auto Mode with 670G at Screening may use Auto Mode:
      - Auto Correction must be turned off
      - Auto Basal setpoint must be set to 120 mg/dL
- Run-in Visit 4: Office Visit Day 14 after Visit 3 (+7 days)
  - Confirm run-in CGM data:
    - Subject demonstrates sensor compliance (i.e. 3,225 glucose sensor data points equivalent to 11.2 days of sensor wear)
  - Continue using study pump with CGM

CIP321 Clinical Investigation Plan				
10813115DOC	Version D	Page 59 of 118		Medtronic

- SmartGuard™ features (Suspend on Low, Predictive Suspend before Low) may be activated
- SAP subjects using Auto Mode with 670G at Screening may use Auto Mode:
  - Auto Correction must be turned off
  - Auto Basal setpoint must be set to 120 mg/dL

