### **Study Period Visits:**

- Visit 5: Office Visit 7-14 days after Visit 4
  - Start AHCL (e.g. Auto Mode feature turned ON with auto-correction)
- Visit 6: Telephone Visit (option of office visit) Day 1 after Visit 5
- Visit 7: Telephone Visit (option of office visit) Day 2 after Visit 5
- Visit 8: Telephone Visit (option of office visit) Day 3 after Visit 5
- Visit 9: Telephone Visit (option of office visit) Day 4 after Visit 5
- Visit 10: Telephone Visit (option of office visit) Day 5 after Visit 5
- Visit 11: Telephone Visit (option of office visit) Day 6 after Visit 5
- Visit 12: Telephone Visit (option of office visit) Day 7 after Visit 5
- Visit 13: Office Visit Day 14 after Visit 5 (± 3 days)
- Visit 14: Telephone Visit Day 21 after Visit 5 (± 3 days)
- Visit 15: Office Visit Day 30 after Visit 5 (± 5 days)
  - Visit 16: Telephone Visit (option of office visit) Day 45 after Visit 5 (± 5 days) • Change Glucose Target
- Visit 17: Office Visit Day 60 after Visit 5 (± 7 days)
  - Visit 18: Office Visit Day 90 after Visit 5  $(\pm 7 \text{ days})$ 
    - End of Study (EOS) Period

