7.2.3 Safety Endpoint – During Study Period and Continued Access

- Serious Adverse Events (SAE)

- Serious Adverse Device Effects (SADE)
- Unanticipated Adverse Device Effects (UADE)
- Incidence of Severe Hypoglycemia
- Incidence of DKA

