7.10 Safety Evaluation

The safety of the study will be evaluated and summarized per all enrolled subjects, including but not limited to the following:

- Serious Adverse Events (SAE)
- Serious Adverse Device Effects (SADE)
- Unanticipated Adverse Device Effects (UADE)
- Incidence of Severe Hypoglycemia
- Incidence of DKA

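### Safety is summarised over everyone who signed consent, so any percentage of subjects with an event in the study period or in continued access would be diluted by people who never entered that period

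*SAP*

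**What the plan says.** SAP 7.1.3 sets one Safety Population for the whole study: "The Safety Population will include all enrolled subjects (subjects who signed inform consent form". SAP 7.10 applies it: "The safety of the study will be evaluated and summarized per all enrolled subjects, including but not limited to the following". The list that follows names SAEs, SADEs and UADEs, and the incidence of severe hypoglycemia and of DKA. *Incidence* is not defined as a count, a percentage or a rate.

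SAP 7.2.3 places these endpoints in two periods: "During Study Period and Continued Access". Protocol 14.7 calls for separate study-phase and continued-access reports, each by age cohort (14-75 and 7-13).

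Protocol 7.2 fixes the moment of enrolment: "Subjects will be considered enrolled in the study upon signing the Informed Consent Form (ICF)/ Assent Form". Protocol 9.3 puts confirmation of eligibility and the start of the study pump at Visit 2, the sensor-wear check at Visit 4, and the study treatment at Visit 5: "Start AHCL (e.g. Auto Mode feature turned ON with auto-correction". Continued access follows, and section 5 of the SAP limits who may enter: "subjects who have completed the entire study period will be given the opportunity to continue using investigational study devices". Protocol 7.1 leaves the number continuing to the subjects' wishes.

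The SAP already has a set defined by entry to the study period, the ITT population (7.1.3), but assigns it to the primary analysis and not to safety. On disposition, SAP 7.1.1 says "The number of subjects enrolled in the study will be presented" and adds a summary of the reasons for discontinuing.

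**The concern.** The denominator is fixed at consent, but the results are reported by period. Under the stated rule, someone who fails screening or leaves during run-in stays in the study-period denominator with no exposure to AHCL in that period. These people, and every completer who declines to continue, also stay in the continued-access denominator. In a percentage of subjects with an event, each of them counts as event-free.

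The purpose of the study is to evaluate the safety of AHCL and then of the 780G system, and the study-phase reports go to FDA with the Pre-Market Application. A period percentage on this denominator would depend partly on how many people failed screening, dropped out early or chose not to continue, none of which describes the device.

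**Working it through.** The documents state no safety percentage and no period denominator, so there is no figure to reproduce. The check is the arithmetic of the stated rule.

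**Inputs**
- Enrolled (consented): up to 350 (SAP section 6).
- Completers: 250, as 125 + 125 (SAP section 6).
- Alternative enrolment: up to 150 to obtain 125 (SAP 7.9.5). Reading this as per cohort, an assumption, gives 2 × 150 = 300.
- Entrants to the study period and to continued access: not given.

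**Formula.** Let k be the subjects with an event in the period, E the entrants and N the consented. The percentage among entrants is k/E. The plan's rule gives k/N = (k/E) × (E/N). The relative understatement is 1 − E/N.

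**Study period.** E lies between the completers and N.
- N = 350, everyone enters: 1 − 350/350 = 0%.
- N = 350, all losses before Visit 5: 1 − 250/350 = 28.6%. This is the ceiling at these numbers.
- N = 350, half the losses before Visit 5 (assumption): 1 − 300/350 = 14.3%.
- N = 300: ceiling 1 − 250/300 = 16.7%; with half the losses before Visit 5, 1 − 275/300 = 8.3%.

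**Continued access.** E cannot exceed the completers.
- N = 350, all 250 continue: 28.6%. This is the minimum.
- N = 300, all 250 continue: 16.7%. This is the minimum.
- 200 continue (assumption): 1 − 200/350 = 42.9%, or 1 − 200/300 = 33.3%.

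**Absolute size within one cohort.** Three subjects with an event are 3/125 = 2.4%, 3/150 = 2.0% or 3/175 = 1.7% (175 assumes 350 split equally). The widest gap is about 0.7 percentage points.

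**What the rule does not change.** Event counts do not use N. Rates per 100 patient-years use exposure, to which non-entrants add nothing in that period. With k = 0 the percentage is 0% on any denominator.

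**Direction.** The understatement assumes that k counts only events in the period. AEs are recorded from consent (protocol 11.1 and 11.3). Suppose one subject has a study-period event and another has an event only in run-in, with N = 350 and E = 300 (illustrative). If both are counted, the plan's percentage is 2/350 = 0.57%, against 1/300 = 0.33% among entrants. That is an overstatement.

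**The case against.** The strongest reply is that no percentage of subjects is promised. *Incidence* is attached only to severe hypoglycemia and DKA; SAEs, SADEs and UADEs are simply named. Protocol 12.2 says that event rates for severe hypoglycemia and DKA will be summarised by age band and overall, and defines an event rate per 100 patient-years. This stands in part: the harm is conditional. But SAP 7.10 does name the people over whom safety is summarised, and the protocol's rate summary sits in the DMC section, refers to a control arm that this study does not have, and is not carried into the SAP. Protocol 14.4.3 speaks of summaries per arm, which in a single-arm study supplies no period denominator.

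A consent-based set also has a real use. The investigational pump starts at Visit 2, and during run-in "SAP subjects using Auto Mode with 670G at Screening may use Auto Mode" (here SAP means sensor-augmented pump). Such a set captures events in those subjects, so it should be kept. It is unsuitable only as the sole denominator for period percentages.

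Continued access might be read as having its own enrolment, because protocol 7.1 speaks of subjects enrolled in that period and a revised consent form is signed. The SAP does not define its set that way. That reading sits badly with protocol 7.2 and would leave the study-period denominator unrepaired.

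Finally, a reader could recover the number of starters from the size of the ITT set and re-base a study-period percentage. That stands. No count of continued-access entrants is specified, so the same cannot be done for that phase.

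**Conclusion.** The point holds in conditional form. If a safety endpoint is reported as a percentage of subjects with an event in a period, the SAP's rule dilutes it by entrants/enrolled. At 250 completers, the relative understatement in the study period is between 0% and 28.6% with 350 enrolled. In continued access it is at least 28.6% with 350 enrolled, or at least 16.7% with 300. These figures rest on planned numbers that are caps on enrolment and on entrant numbers that the documents do not give.

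Three stronger readings are tempting and are not supported:
- That reported safety percentages would always be too low. They would not be if every consented subject entered the period, if there were no events, or if run-in events remained in the numerator.
- That disposition gives only the number enrolled. It also gives the reasons for discontinuing; what is missing is a count of continued-access entrants.
- That the study's inferences are compromised. No hypothesis test or stopping rule uses these summaries. The effect is confined to descriptive safety percentages in the final reports.

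It is still worth correcting before the reports are produced: safety is the stated purpose, a better denominator for the study period already exists in the SAP, and fixing it in advance removes a later choice.

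**What to change.** - **SAP 7.1.3 and 7.10:** use the ITT set, meaning subjects who entered Auto Mode in the study period (at or after Visit 5), as the denominator for study-period safety percentages. Use subjects who entered continued access for that phase. Give each by age cohort (7-13 and 14-75).
- **Same sections:** keep the all-consented set for AE listings, and show run-in events separately so that they do not enter study-period numerators.
- **SAP 7.1.1:** add the number of subjects entering each period.
- **SAP safety tables:** carry over the events-per-100-patient-years summary from protocol 12.2, worded for a single arm.

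The cost is wording in three SAP sections, a few more table columns and a rate line. No new data are needed. Period percentages may look slightly less favourable than on the all-consented denominator.
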